Duotherm Usability Study

IRB Approved: 6/11/2020

The purpose of this focus group is to evaluate the feasibility of the DuoTherm device in treating low back pain.

Methods: A convenient sample of up to 20 patients with acute or chronic low back pain (LBP) will be recruited in two tranches for this study. Exclusionary criteria will include: less than 18 years of age; pregnancy; cancer; radicular pain likely reflecting a surgical or mechanical problem; BMI greater than 30 (device won't fit); sensitivity to cold or vibration (e.g. Raynaud's or Sickle Cell Disease); diabetic neuropathy rendering a patient unable to determine if the device is too hot; new neurologic deficits, skin lesions over the low back area; the inability to apply DuoTherm device. Up to 10 participants will be recruited to provide feedback on the device at the conclusion of their treatment. Upon agreement, consent will be obtained, and participants will complete all study paperwork and rate their current low back pain on a 0 – 10 Visual Analog Scale. Participants will be given instructions on how to use the DuoTherm. They will then be given up to 20 minutes to use the device on the setting of their choosing.

Study personnel will give enrolled patients a choice of heat, cold, or no thermal intervention. A frozen solid ice pack (VibraCool®, Pain Care Labs, Atlanta Georgia) with 4-22g sections or a microwaved single chamber 150g clay pack will be inserted behind the metal plate, and the device attached to the patient over a single layer of thin clothing. Patients will be instructed how to toggle between 12 different vibration frequency patterns, with 5 different intensity settings for each pattern. Patients will rate their pain again using a 10cm 0-10 Visual Analog Scale and chose the mechanical stimulation pattern they preferred. In addition, participants will comment on usability, mechanical stimulation pattern preference, comfort, suggested improvements, whether they would recommend the device, pain relief on an additional 1-7 Likert scale ranging from "No relief" to "Complete relief".

After using the device, they will complete a device specific questionnaire. All participants who complete the questionnaires will be given a \$25 gift card for participating. After 10 participants have completed the study, the results will be discussed with the manufacturer and any issues will be addressed by revising the prototype. Additionally, investigators will evaluate the device instructions and revise as needed. The new prototype and instructions would then be evaluated on an 2nd cohort of up to 10 participants using the same protocol.

Data Collection:

Background Information: The background information questionnaires will be administered at the beginning of the focus group. Data collected by self-report with this instrument will include of age, gender, current pain medication usage, history of low back pain, and experience with pain modalities.

Statistical Analysis Plan:

Sample Size: 32 Patients have already tried the early version of the device. In addition to pain relief, we anticipate the revisions will improve the device, and are primarily interested in collecting information about comfort, usability, and choice of thermal interventions device. Prior studies with the device showed a reduction in pain of 3 +/-1 on a ten point scale. The VibraCool device with only cold and a single vibration frequency had an effect size of 0.56.

The study number will be powered by pain ratings. We anticipate the device will reduce pain by 2 after 20 minutes of use in patients with a pain score of 4 or more. If the initial pain is 5 +/- 2, with an alpha of .05 a sample size of 8 will have 80% power to detect a difference of 2. A sample size of 11 will have 90% chance.

Analysis:

Averages and standard deviations will be reported for age (<40 years and ≥40 years), cold/hot treatment preference, sex, device plate configuration, and pain chronicity. Pain scores in cm on VAS will be reported with standard deviations and t-test p values before and after device, and total percent pain relief will be reported.

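### The sensory-loss exclusion is narrower than its own stated reason, so long-standing non-diabetic numbness at the application site does not exclude a patient from the heat or cold pack

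*Combined protocol and SAP*

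**What the plan says.** The Methods section recruits "patients with acute or chronic low back pain (LBP", so long-standing conditions are in scope. Four of its exclusions bear on sensation or nerve function:

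- "diabetic neuropathy rendering a patient unable to determine if the device is too hot; new neurologic deficits", which are two adjacent items;
- "sensitivity to cold or vibration (e.g. Raynaud's or Sickle Cell Disease", closing a parenthesis of examples;
- "radicular pain likely reflecting a surgical or mechanical problem".

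The list ends with "the inability to apply DuoTherm device", which is about handling the device and not about feeling it.

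On exposure, the same section states: "Study personnel will give enrolled patients a choice of heat, cold, or no thermal intervention". The cold source is a solidly frozen pack. The heat source is a 150 g clay pack warmed in a microwave, with no temperature given. Either pack sits behind the metal plate, and the device is worn over one thin layer of clothing for at most 20 minutes. The background questionnaire under Data Collection covers demographics, pain medication, back pain history and past use of pain modalities. It lists no item on sensation.

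**The concern.** An exclusion that states its reason can be tested against that reason. Here the reason is that the patient cannot tell when the device has become too hot. That inability has the same consequence whether it comes from diabetes or from another cause, and whether it is recent or old. The wording nevertheless admits one cause only, and the only other neurologic item is limited to recent loss.

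Two patients with the same functional deficit at the application site can therefore be treated differently, one excluded and the other enrolled and offered heat or cold. What is at stake is participant safety. The plan thought the patient's own perception important enough to make its loss an exclusion, but the protection does not reach everyone who lacks that perception. On the cold side, no criterion names inability to feel excessive cold, although a frozen pack is one of the options.

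**Working it through.** No figure in the plan bears on this point, so there is nothing to reproduce. The check is textual. Take a patient with chronic low back pain and a long-standing, stable, non-diabetic area of numbness over the low back, with no other excluding condition. Then go through the ten exclusions listed in the Methods.

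1. Age under 18: not met.
2. Pregnancy: not met.
3. Cancer: not met.
4. Radicular pain with a likely surgical or mechanical cause: the item names pain. It would remove some patients whose numbness accompanies such pain, but not a patient on account of numbness alone.
5. BMI above 30: not met.
6. Sensitivity to cold or vibration: the examples given, Raynaud's and sickle cell disease, are adverse reactions to cold. Failing to feel cold is a different condition and is not named.
7. Diabetic neuropathy with inability to judge heat: the function matches but the cause does not. Not met.
8. New neurologic deficits: the numbness is old. Not met.
9. Skin lesions over the low back: numb skin need not carry a lesion. Not met.
10. Inability to apply the device: not met.

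The patient meets none of the ten and is eligible as the list is written.

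Next, set eligibility beside exposure. Once enrolled, the patient chooses heat, cold or neither. Nothing in the Methods makes that choice depend on sensation at the site, and neither the Methods nor the Data Collection section describes a sensory test. The eligible patient can therefore receive either pack.

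Finally, compare this patient with a diabetic patient who cannot judge heat at the same site. Item 7 excludes the diabetic patient from the whole study, and so from the frozen pack as well as the heated one. The heat-only wording therefore does not let that patient through to cold. It matters for a patient who can judge heat but not cold, and for the patient above, whom no item reaches for either pack.

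**The case against.** The strongest case on the other side has five parts.

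*The items do not conflict.* This stands. The diabetic item and the item on new deficits are separate and compatible. The mismatch is between one item's wording and that item's own reason.

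*Other features limit exposure.* This also stands. The pack lies behind a plate, clothing intervenes, use is capped at 20 minutes, skin lesions exclude, instructions are given, and the patient may decline both packs. A reader might infer that the diabetic item is the plan's only protection against an unnoticed hot pack, and the text does not support that. These features limit exposure for everyone, however. They do not screen for loss of sensation and do not change who is eligible.

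*The text may be incomplete.* The list is introduced in terms that need not be exhaustive, consent pages are absent from the available copy, and the instructions for use are mentioned but not reproduced. Thermal warnings could appear there. Even so, the available text contains no wider sensory criterion and no investigator-discretion exclusion, and a warning elsewhere would not be an eligibility rule.

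*The frequency is unknown.* This stands in full. A reader might want to put a probability on enrolling such a patient, but the answer depends wholly on an assumed prevalence. With the maximum of 20 patients, assuming that 2% to 10% have any old sensory loss at the site gives 1 − 0.98^20 = 0.33 to 1 − 0.90^20 = 0.88. Assuming that 0.1% to 0.5% are functionally unable to judge heat gives 1 − 0.999^20 = 0.02 to 1 − 0.995^20 = 0.10. Neither range has a basis in the documents, and the first counts a wider condition than the one the criterion names.

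*Widening the exclusion is a clinical decision and narrows the sample.* Who may safely receive heat or cold is for the investigators. Patients with altered sensation are also plausible users of the device, so excluding them has a price. This shapes the fix but does not remove the mismatch.

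**Conclusion.** The point holds as a gap in the wording of eligibility. One identifiable type of patient, with the same functional deficit that the plan itself treats as a reason to exclude, passes all ten listed exclusions and may be given either pack. The conclusion rests on reading the list literally and on no wider criterion existing in material not available here.

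Its size cannot be given as a probability. It should be acted on because it concerns participant safety and is cheap to correct, not because such patients are shown to be common.

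Two stronger readings should be resisted. A reader might infer that participants are being harmed, but the documents show who is eligible, not what happened to anyone. A reader might also infer that enrolling such patients distorts the comfort and thermal-choice findings, which the Sample Size paragraph names as the main interest. One such patient would be 1/20 = 5% of a full sample, or 1/10 = 5%/0.5 = 10% of a full first cohort, but the documents show no direction of bias and no conclusion that would change.

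**What to change.** The sponsor should reconcile three parts of the Methods: the diabetic-neuropathy item and the functional reason written into it, the item restricted to new neurologic deficits, and the heat and cold options offered to every enrolled patient. After reconciliation, the sensory criterion should turn on the ability to judge device temperature at the application site and not on one cause. The text should also make clear how long-standing loss and the cold pack are meant to be handled. One screening question before enrolment would check it. How much loss matters, and for which pack, is for the investigators to set.

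The cost is one line in the exclusion list and one question at screening. The downside is that a few otherwise eligible patients may be excluded, which slightly narrows the group from which usability feedback is drawn. The second cohort follows the same protocol, so a single change made at the outset covers both.

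### Does an undefined, uncounted exclusion for inability to apply the device leave a hole in the usability results?

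*Combined protocol and SAP*

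**What the plan says.** The opening statement gives the purpose as to "evaluate the feasibility of the DuoTherm device in treating low back pain". The Sample Size section adds that the main interest is in comfort, ease of use and which thermal option patients choose.

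The exclusion list in Methods contains two items tied to the device: "BMI greater than 30 (device won't fit" and, as the last item, "the inability to apply DuoTherm device". The second has no definition, no named assessor and no timing.

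After consent and the first pain rating, "Participants will be given instructions on how to use the DuoTherm". The next paragraph says "Study personnel will give enrolled patients a choice of heat, cold, or no thermal intervention"; a pack is then inserted, "the device attached to the patient over a single layer of thin clothing", and patients learn how to switch patterns. Who attaches the device is not stated.

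Usability information comes from participants' comments and from a questionnaire: "After using the device, they will complete a device specific questionnaire". Once ten participants have finished, "the results will be discussed with the manufacturer and any issues will be addressed by revising the prototype", and the investigators also review the instructions. The Analysis section lists descriptive breakdowns, pain scores and percent relief. It has no item for exclusions or failed applications.

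**The concern.** A usability study seems to screen out its most telling failures. Someone who cannot get the device on either never enters the study or does not reach the questionnaire, which follows use. The prototype and instructions are to be revised after the first cohort, so even one outright failure would be useful to the manufacturer at that point. If such cases are neither defined nor counted, the report cannot say how many there were, and a reader might take the results to cover everyone with low back pain. The passive wording about attachment adds a second doubt: if staff attach the device, self-application is not tested at all.

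**Working it through.** **1. Where the criterion stands.** The other exclusions are age, pregnancy, cancer, radicular pain, BMI, cold or vibration sensitivity, diabetic neuropathy, new neurologic deficits and skin lesions. All are states the patient has before any contact with the device. The list comes before recruitment, consent, instructions and use. Read in sequence, inability to apply the device is one more limit checked at entry.

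**2. What each reading does to the planned results.**

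- *Screening limit.* The patient is not enrolled and was never going to give usability data. No observation is lost. What is absent is a tally of people screened out.
- *Failed attempt after consent.* The questionnaire would not be reached. The sentence asking participants to comment on usability and improvements is not expressly tied to successful application, although it follows the use session. The investigators' review of the instructions is planned in any case. A failure could be picked up by these routes, but would have no structured record.
- *Staff attach the device.* Self-application is then not under test and there is no self-application failure to count. Results describe use once the device is on.

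Under none of these does a planned summary (comfort, preference, recommendation, pain before and after) take a wrong value for the people it describes.

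**3. How much a count could show under the second reading.** The documents give no failure rate, so take p = 5%, 10%, 20% and 30% as assumptions. The chance of at least one failure in ten attempts is 1 − (1 − p)^10:

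| p | (1 − p)^10 | chance of at least one |
|---|---|---|
| 5% | 0.599 | 40% |
| 10% | 0.349 | 65% |
| 20% | 0.107 | 89% |
| 30% | 0.028 | 97% |

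If ten attempts show no failure, the exact two-sided 95% upper limit is 1 − 0.025^(1/10) = 0.308, that is 31%. So a failure could well occur and be worth telling the manufacturer about, but a cohort of ten cannot estimate the rate usefully. The cohorts should not be pooled for this, since the second tests a revised prototype and instructions.

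**4. The pain analysis.** The plan's sample sizes follow from the two-sided normal approximation with difference 2 and SD 2. The SD is given for initial pain and is used here for the change.

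- 80% power: ((1.960 + 0.842) × 2/2)² = 7.85, so 8.
- 90% power: ((1.960 + 1.282) × 2/2)² = 10.51, so 11.

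Neither figure depends on how the criterion is defined. If enrolled patients who could not apply the device took places under the cap, pairs would be lost. With the same SD and a two-sided paired t-test, power is 98.9% at 20 pairs and 97.2% at 17. In one cohort analysed alone it would be 80% at 10 pairs and 60% at 7, but the plan does not call for a t-test in each cohort.

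**The case for a change.** The best case for a change is that failure to apply a device is a primary usability outcome, that the wording leaves open whether failures after instructions are discarded, and that the remedy costs almost nothing: a definition, a line on who attaches the device, and a count passed to the manufacturer. The factual parts stand. The criterion is undefined, attachment is described in the passive, and no count is planned. Reporting the number of people who could not apply the device would be good practice.

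The inference that failures have no way into the results does not stand. It needs the less natural reading of an entry criterion, it needs patients rather than staff to attach the device, and it sets aside the comments and the review of instructions. Counting BMI exclusions as well would add little, because the protocol already says why those patients are left out. A per-cohort count would also run into the limit of up to ten participants, since the plan does not say whether someone who fails an attempt uses a place. The remedy therefore adds detail; it does not correct a rule or a figure.

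**Conclusion.** No change to the plan is needed. This is a gap in detail that those running and reporting a small focus-group study can fill sensibly: describe the sample as people able to use the device, say who attached it, and mention anyone who could not. The stake is one descriptive count in a convenience sample of up to 20. Ten attempts without a failure would leave anything from 0% to 31% possible. The sample sizes of 8 and 11 and the planned summaries are unaffected.

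This rests on reading the criterion as a screening limit, which its place in the list supports but the text does not state. If failed attempts after consent were treated as exclusions, outright failures would lack a structured record, and the report should then not claim that all participants could apply the device. Even so, the comfort, preference and pain results would remain valid for those who used it.

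### Must the Analysis be changed because it gives no summary for comfort and usability and labels thermal choice only as cold/hot?

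*Combined protocol and SAP*

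**What the plan says.** The SAP's Sample Size section states that the investigators "are primarily interested in collecting information about comfort, usability, and choice of thermal interventions device". The same sentence opens with "In addition to pain relief, we anticipate the revisions will improve the device", directly after a remark that 32 patients have already tried an early version.

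Methods describes how these data arise. On thermal choice: "Study personnel will give enrolled patients a choice of heat, cold, or no thermal intervention". On feedback: "Up to 10 participants will be recruited to provide feedback on the device at the conclusion of their treatment", and "participants will comment on usability, mechanical stimulation pattern preference, comfort", among other topics. A device-specific questionnaire follows use of the device. After the first 10 participants, "the results will be discussed with the manufacturer and any issues will be addressed by revising the prototype"; the instructions are reviewed as well, and the new prototype and instructions go to a second cohort of up to 10 under the same protocol.

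The Analysis paragraph has two sentences. The first begins "Averages and standard deviations will be reported for age", split at 40 years, and continues with "cold/hot treatment preference, sex, device plate configuration, and pain chronicity". The second covers VAS pain before and after the device, with standard deviations, t-test p values and percent relief.

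**The concern.** Set against the stated main interest, the Analysis looks incomplete in two ways.

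- **Comfort and usability.** These are two of the three topics of main interest, and neither has a summary method. The questionnaire is not mentioned either. Cohort is not among the five listed factors, although the second cohort tests a revised device. The documents do not say whether plate configuration identifies the prototype.
- **Thermal choice.** Methods offers three options and the Analysis names two. Anyone who declines both packs has no named group, so the share who want no pack at all might never be reported.

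If this mattered, a reader of the results could not judge the second prototype from the feedback, and an answer the study set out to collect would be lost.

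**Working it through.** **1. The plan's own figures.** The only calculation in the SAP concerns pain: 8 patients for 80% power and 11 for 90%, to detect a difference of 2 with SD 2 and alpha 0.05. Take the SD as that of the change, with two-sided alpha and the normal approximation. Then n = (SD × (z for alpha/2 + z for power) / difference)²:

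- 80% power: (2 × (1.960 + 0.842) / 2)² = 7.85, rounded up to 8.
- 90% power: (2 × (1.960 + 1.282) / 2)² = 10.51, rounded up to 11.

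Both figures reproduce on that approximation. Comfort, usability and thermal choice do not enter the formula, so the gap cannot affect the sample size.

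**2. The texts side by side.**

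| Topic | Collected | Line in Analysis | Other stated use |
|---|---|---|---|
| Thermal choice | Heat, cold or none (Methods) | Yes, labelled cold/hot | None stated |
| Comfort, usability | Comments (Methods) | None | Manufacturer discussion, prototype revision |
| Device questionnaire | After use (Methods) | None | None named separately |

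The omissions are real. The question is whether any of them would lead an analyst to a wrong or missing result.

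**3. The cold/hot label.** The listing sentence puts thermal preference beside age band, sex, plate configuration and chronicity. The natural reading is that an outcome is averaged within each subgroup. On that reading the defect is one unnamed level. Nothing says that patients without a pack are dropped, and if group sizes are shown, their number is the total minus the other two groups.

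The other reading, averaging a 0/1 code, would lose the three-way split. Suppose 8 of 20 choose cold (illustrative). The mean is 8/20 = 0.40 and the SD is √(0.4 × 0.6 × 20/19) = 0.503, whether 0 or all 12 of the others chose no pack. That is a valid criticism of an analysis nobody is likely to run.

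**4. What by-cohort counts would add.** Suppose a revision leaves a problem unfixed, each affected user would report it, and the second cohort is a full 10. The chance that nobody mentions it is (1 − p)^10. The documents give no p, so the rates below are assumed.

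| Assumed p | Chance of 0 of 10 |
|---|---|
| 10% | 0.349 |
| 20% | 0.107 |
| 30% | 0.028 |

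The exact two-sided 95% upper limit for 0 of 10 is 1 − 0.025^(1/10) = 0.308. For a 50% share, the exact 95% interval is 19–81% at n = 10 and 27–73% at n = 20.

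All of these follow from having 10 or 20 people. A promised table would change none of them. With counts by cohort in hand, a reader still could not separate a fixed problem from one that happened not to come up; counts would only make the imprecision visible.

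**The case for a change.** The strongest case for a change is that the plan specifies summaries for pain and subgroups but not for what it calls its main interest. Discussion with the manufacturer is a use of results, not a method of summary, and it is described only after the first cohort. A statement of denominators would stop silence in the second cohort being read as success. The no-pack share answers a real design question. The cost is a few words and a table or two.

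Some of this stands. The text is thinner than it should be, and three thermal categories with the number responding would be better wording. Three things limit it:

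- The second cohort is there to evaluate the new prototype; the documents promise no comparison between cohorts.
- The sentence about revisions follows the mention of the early version, so it may refer to changes made before this study. It is weak evidence of an expected difference between the cohorts.
- The questionnaire's response format is not given in the documents, so a more specific summary rule could not be written from them.

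**Conclusion.** No change to the plan is needed. The gap is confirmed as a matter of text: there is no line for comfort, usability or the questionnaire, and there are two named thermal levels where three are offered. It is missing descriptive detail that an analyst would fill sensibly by counting heat, cold and none over all participants and summarising the comments and questionnaire with the number responding.

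Its effect on the pain result and the sample size is nil. The imprecision of the feedback (an upper limit of 31% after 0 of 10) belongs to the cohort size and would remain under any wording.

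The conclusion rests on three assumptions: that the choice of no pack is recorded when made, that the listed factors are subgroup labels and not coded averages, and that the feedback is formative, as the focus-group purpose and the revision step indicate. If the sponsor planned a formal comparison of prototypes on usability, the matter would be different, but the documents describe none.
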